### 5.1.2 Subject Exclusion Criteria

The subject must be excluded from participating in the trial if the subject:

1. Has a diagnosis of immunodeficiency or is receiving systemic steroids (less than or equal to 10 mg prednisone equivalent at time of start of treatment is ok) therapy or any other form of immunosuppressive therapy within 7 days prior to the first dose of trial treatment
2. If they have brain metastases located in the brain stem (including midbrain, pons, or medulla);
3. Inability to undergo MRI evaluation for treatment planning and follow-up
4. Is currently participating and receiving study therapy or has participated in a study of an investigational agent and received study therapy or used an investigational device within 4 weeks of the first dose of treatment. Has a diagnosis of immunodeficiency or is receiving systemic steroids (less than or equal to 10 mg prednisone equivalent at time of start of treatment is ok) therapy or any other form of immunosuppressive therapy within 7 days prior to the first dose of trial treatment.
5. Has a known history of active TB (Bacillus Tuberculosis)
6. Hypersensitivity to pembrolizumab or any of its recipients.
7. Has had prior chemotherapy, targeted small molecule therapy, or radiation therapy within 2 weeks prior to study Day 1 or who has not recovered (i.e.,  $\leq$  Grade 1 or at baseline) from adverse events due to a previously administered agent.
  - Note: Subjects with  $\leq$  Grade 2 neuropathy are an exception to this criterion and may qualify for the study.
  - Note: If subject received major surgery, they must have recovered adequately from the toxicity and/or complications from the intervention prior to starting therapy.
8. Has a known additional malignancy that is progressing or requires active treatment. Exceptions include basal cell carcinoma of the skin or squamous cell carcinoma of the skin that has undergone potentially curative therapy or in situ cervical cancer.
9. Has active autoimmune disease that has required systemic treatment in the past 2 years (i.e. with use of disease modifying agents, corticosteroids or immunosuppressive drugs). Replacement therapy (eg., thyroxine, insulin, or physiologic corticosteroid replacement therapy for adrenal or pituitary insufficiency, etc.) is not considered a form of systemic treatment.
10. Has known history of (non-infectious) pneumonitis that required steroids (less than or equal to 10 mg prednisone equivalent at time of start of treatment is ok) or current pneumonitis.
11. Has an active infection requiring systemic therapy.
12. Has a history or current evidence of any condition, therapy, or laboratory abnormality that might confound the results of the trial, interfere with the subject's participation for the full duration of the trial, or is not in the best interest of the subject to participate, in the opinion of the treating investigator.

13. Has known psychiatric or substance abuse disorders that would interfere with cooperation with the requirements of the trial.
14. Is pregnant or breastfeeding, or expecting to conceive or father children within the projected duration of the trial, starting with the pre-screening or screening visit through 120 days after the last dose of trial treatment.
15. Has a known history of Human Immunodeficiency Virus (HIV) (HIV 1/2 antibodies).
16. Has known active Hepatitis B (e.g., HBsAg reactive) or Hepatitis C (e.g., HCV RNA [qualitative] is detected).
17. Has received a live vaccine within 30 days of planned start of study therapy.

*Note: Seasonal influenza vaccines for injection are generally inactivated flu vaccines and are allowed; however intranasal influenza vaccines (e.g., Flu-Mist®) are live attenuated vaccines, and are not allowed.*

## 6.0 ADMINISTRATION OF STUDY PHARMACEUTICAL

In 2015, FDA approved Pembrolizumab (Keytruda) for the treatment of advanced melanoma and NSCLC patients; Pembrolizumab is a monoclonal antibody that targets the PD-1 receptor. Programmed death 1 (PD-1) (or CD279) is part of the CD28 family of proteins, which includes CTLA-4 and ICOS, that regulate T cell activity. PD-1 is a glycoprotein receptor that can be expressed on the surface of T cells, B cells and myeloid cells (monocytes and dendritic cells). In T cells, PD-1 expression is primarily induced by T cell receptor (TCR) engagement and ligation with PD-L1 and PD-L2, expressed on antigen presenting cells, and induces an inhibitory signal that antagonizes TCR signaling and other important pathways necessary for optimal T cell activation. Clinical trials with Pembrolizumab in advanced melanoma and NSCLC patients lead to approval by the FDA. The recommended dose of Keytruda is 2mg/kg administered as IV infusion over 30 minutes every 3 weeks +/- 7 days until disease progression, or unacceptable toxicity. Alternative dosing regimens are also available.

The IV treatment to be used in this trial is outlined below in **Table 5**. Radiation treatment outline/table is listed in 10.0

**Table 5 Pembrolizumab Treatment**

Drug	Dose	Dose Frequency	Route of Administration	Regimen/Treatment Period	Use
Pembrolizumab	200 mg	Q3W	IV infusion	Day 1 of each 3 week cycle	Experimental

### 6.1.1 Dose Selection

#### 6.1.1.1 Dose Selection

Patients will receive pembrolizumab 200 mg. Pembrolizumab will be delivered over a 30-minute period every 3 weeks +/- 7 days until at least 2 year, progression of disease, and/or unacceptable toxicity at the discretion of the treating physician. Infusions should be given over 30 minutes (not bolus or IV push).

The rationale for selection of the dose (200 mg) to be used in this trial is provided in Section 4.0 – Background and Rationale.

### **6.1.1.2 Pembrolizumab Dose Calculation**

Calculate Total Dose as follows: 200 mg;

Calculate Total Infusion Volume as follows:

$$\text{Total dose in mg} \div 10 \text{ mg/mL} = \text{infusion volume in mL}$$

Calculate Rate of Infusion as follows:

$$\text{Infusion volume in mL} \div 30 \text{ minutes} = \text{rate of infusion in mL/min.}$$

For example, a patient weighing 75 kg (165 lb.) would be administered 200 mg of pembrolizumab with an infusion volume of 20 mL ( $2000 \text{ mg} \div 10 \text{ mg/mL} = 20 \text{ mL}$ ) at a rate of approximately 0.66 mL/min in 30 minutes ( $20 \text{ mL} \div 30 \text{ minutes}$ ).

### **6.1.2 Timing of Dose Administration**

Trial treatment should be administered on Day 1 of each cycle after all procedures/assessments have been completed as detailed on the Trial Flow Chart (Section 6.0). Trial treatment may be administered up to 3 days before or after the scheduled Day 1 of each cycle due to administrative reasons.

All trial treatments will be administered on an outpatient basis.

Pembrolizumab 200 mg will be administered as a 30 minute IV infusion every 3 weeks +/- 7 days. Sites should make every effort to target infusion timing to be as close to 30 minutes as possible. However, given the variability of infusion pumps from site to site, a window of -5 minutes and +10 minutes is permitted (i.e., infusion time is 30 minutes: -5 min/+10 min).

The Pharmacy Manual contains specific instructions for the preparation of the pembrolizumab infusion fluid and administration of infusion solution.

### **6.1.3 Trial Blinding/Masking**

This is an open-label trial; therefore, the Sponsor, investigator and subject will know the treatment administered.

## **6.2 Randomization Allocation**

Not applicable

## **6.3 Stratification**

Not applicable

## **6.4 Concomitant Medications/Vaccinations (allowed & prohibited)**

Medications or vaccinations specifically prohibited in the exclusion criteria are not allowed during the ongoing trial. If there is a clinical indication for one of these or other medications or vaccinations specifically prohibited during the trial, discontinuation from trial therapy or vaccination may be required. The sponsor-investigator should discuss any questions regarding this with the Merck Clinical team. The final decision on any supportive therapy or vaccination rests with the sponsor-investigator and/or the subject's primary physician.

### **6.4.1 Acceptable Concomitant Medications**

All treatments that the investigator considers necessary for a subject's welfare may be administered at the discretion of the investigator in keeping with the community standards of medical care. All concomitant medication will be recorded on the case report form (CRF) including all prescription, over-the-counter (OTC), herbal supplements, and IV medications and fluids. If changes occur during the trial period, documentation of drug dosage, frequency, route, and date may also be included on the CRF.

All concomitant medications received within 28 days before the first dose of trial treatment and within 30 days after the last dose of trial treatment should be recorded. Concomitant medications administered 30 days after the last dose of trial treatment should be recorded for SAEs and ECIs as defined in Section 13.2.3.2.

### **6.4.2 Prohibited Concomitant Medications**

Subjects are prohibited from receiving the following therapies during the Screening and Treatment Phase of this trial:

- Antineoplastic systemic chemotherapy or biological therapy
- Immunotherapy not specified in this protocol
- Chemotherapy not specified in this protocol
- Investigational agents other than pembrolizumab
  
- Live vaccines within 30 days prior to the first dose of trial treatment and while participating in the trial. Examples of live vaccines include, but are not limited to, the following: measles, mumps, rubella, varicella/zoster, yellow fever, rabies, BCG, and typhoid vaccine.
  
- Systemic glucocorticoids for any purpose other than to modulate symptoms from an event of clinical interest of suspected immunologic etiology. The use of physiologic doses of corticosteroids (less than or equal to 10 mg of prednisone equivalent at time of start of treatment is ok). Anything more than this may be approved after consultation with the Sponsor.

Subjects who, in the assessment by the investigator, require the use of any of the aforementioned treatments for clinical management should be removed from the trial. Subjects may receive other medications that the investigator deems to be medically necessary.

The Exclusion Criteria describes other medications which are prohibited in this trial. There are no prohibited therapies during the Post-Treatment Follow-up Phase.

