## 10.2 Subject Withdrawal/Discontinuation Criteria

Subjects may withdraw consent at any time for any reason or be dropped from the trial at the discretion of the investigator should any untoward effect occur. In addition, a subject may be withdrawn by the sponsor-investigator if enrollment into the trial is inappropriate, the trial plan is violated, or for administrative and/or other safety reasons

A subject must be discontinued from the trial for any of the following reasons:

- The subject or legal representative (such as a parent or legal guardian) withdraws consent.
- Confirmed extra-cranial radiographic disease progression
- Unacceptable adverse experiences as described in section 7, 8, and 9.
- Intercurrent illness that prevents further administration of treatment
- Investigator's decision to withdraw the subject
- The subject has a confirmed positive serum pregnancy test
- Noncompliance with trial treatment or procedure requirements
- The subject is lost to follow-up
- Completed at least 24 months of uninterrupted treatment with pembrolizumab or 35 administrations of study medication, or whichever occurs last;  
*Note: 24 months of study medication is calculated from the date of first dose. Subjects who stop pembrolizumab after 24 months may be eligible for up to one year of additional study treatment at the discretion of their treating physician, especially if their disease is clinically stable;*
- Administrative reasons
- Confirmed radiographic disease progression per RECIST criteria.
  - a. *Note: A subject may be granted an exception to continue on treatment with confirmed radiographic progression if clinically stable or clinically improved, please see Section 6.5*

The End of Treatment and Follow-up visit procedures are listed in Section 12 (Protocol Flow Chart) and Section 13. After the end of treatment, each subject will be followed for 30 days for adverse event monitoring (serious adverse events will be collected for 90 days after the end of treatment as described in Section 13.2.3.1). Subjects who discontinue for reasons other than progressive disease will have post-treatment follow-up for disease status until disease progression, initiating a non-study cancer treatment, withdrawing consent or becoming lost to follow-up. After documented disease progression each subject will be followed by telephone for overall survival until death, withdrawal of consent, or the end of the study, whichever occurs first.

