#### **13.1.1.6.3 Subsequent Anti-Cancer Therapy Status**

The investigator or qualified designee will review all new anti-neoplastic therapy initiated after the last dose of trial treatment. If a subject initiates a new anti-cancer therapy within 30 days after the last dose of trial treatment, the 30-day Safety Follow-up visit must occur before the first dose of the new therapy. Once new anti-cancer therapy has been initiated the subject will move into survival follow-up.

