#### **13.1.1.13 Withdrawal/Discontinuation**

When a subject discontinues/withdraws prior to trial completion, all applicable activities scheduled for the final trial visit should be performed at the time of discontinuation. Any adverse events which are present at the time of discontinuation/withdrawal should be followed in accordance with the safety requirements outlined in Section 8.0 - Assessing and Recording Adverse Events. Subjects who a) attain a CR or b) complete at least 24 months of treatment with pembrolizumab may stop taking the drug and discontinue the trial, at the discretion of the treating physician. After discontinuing treatment following assessment of CR, these subjects should return to the site for a Safety Follow-up Visit and then proceed to the Follow-Up Period of the study.

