#### **13.1.3.2.1 Safety Follow-Up Visit**

The mandatory Safety Follow-Up Visit should be conducted approximately 30 days after the last dose of trial treatment or before the initiation of a new anti-cancer treatment, whichever comes first. All AEs that occur prior to the Safety Follow-Up Visit should be recorded. Subjects with an AE of Grade > 1 will be followed until the resolution of the AE to Grade 0-1 or until the beginning of a new anti-neoplastic therapy, whichever occurs first. SAEs that occur within 90 days of the end of treatment or before initiation of a new anti-cancer treatment should also be followed and recorded. Subjects who are eligible for retreatment with pembrolizumab (as described in Section 6.5) may have up to two safety follow-up visits, one after the Treatment Period and one after the Second Course Phase.

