#### **13.1.2.3 Follow-up Visits**

Subjects who complete treatment after 2 years or discontinue trial treatment for a reason other than disease progression should be assessed every 12 weeks ( $84 \pm 14$  days) or at physicians' discretions by radiologic imaging to monitor disease. Subjects who show disease progression after the initial week 12 scan must have another assessment 4-6 weeks later by radiologic imaging to confirm evidence of disease progression. If disease progression is evident, treatment should be discontinued and subject should be assessed every 12 weeks ( $84 \pm 14$  days) by radiologic imaging to monitor disease status. Every effort should be made to collect information regarding disease status until the start of new anti-neoplastic therapy, disease progression, death, end of the study or if the subject begins retreatment with pembrolizumab as detailed in Section 6.5. Information regarding post-study anti-neoplastic treatment will be collected if new treatment is initiated.

Subjects who are eligible to receive retreatment with pembrolizumab according to the criteria in Section 6.5 will move from the follow-up phase to the Second Course Phase when they experience disease progression. Details are provided in Section 13.1.3.4 for Retreatment.

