#### **13.1.2.4.1 Survival Follow-up**

Once a subject experiences confirmed disease progression or starts a new anti-cancer therapy, the subject moves into the survival follow-up phase and should be contacted by telephone every 12 weeks to assess for survival status until death, withdrawal of consent, or the end of the study, whichever occurs first.

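### After new anti-cancer therapy or confirmed progression, follow-up shrinks to survival telephone calls, yet CNS toxicity is still due at 6 and 12 months and 14.3.1 keeps unread patients in its denominator

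*Combined protocol and SAP*

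**What the plan says.** **Follow-up after new therapy or progression**
- Section 13.1.1.6.3: "Once new anti-cancer therapy has been initiated the subject will move into survival follow-up". If the new therapy starts within 30 days of the last dose, the 30-day safety visit comes first.
- Section 13.1.2.4.1 applies this to new therapy and also to confirmed progression alone. Such patients "should be contacted by telephone every 12 weeks to assess for survival status".
- Section 10.2 gives patients who stop for other reasons "post-treatment follow-up for disease status until disease progression, initiating a non-study cancer treatment", and follows patients by telephone for survival after documented progression.
- Section 13.1.2.3 differs. Once progression is confirmed and treatment stopped, it calls for imaging every 12 weeks, but it also asks sites to "collect information regarding disease status until the start of new anti-neoplastic therapy, disease progression, death, end of the study".
- Section 6.4.2 says that, in the screening and treatment phase, subjects who "require the use of any of the aforementioned treatments for clinical management should be removed from the trial". Its parent, section 6.4, says only that "discontinuation from trial therapy or vaccination may be required".

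**Readings the plan requires**
- Section 14.1.1 sets the DLT at 3 months after cycle 1, day 1. An arm stops at 3 or more DLTs in 6 and expands at 2 or fewer.
- Sections 2.3 and 14.1.2 record symptomatic radiation necrosis at 6 and 12 months.
- The flow chart (12.1) lists Grade 3 CNS readings at 3, 6 and 12 months. None of these places makes an exception for patients on telephone contact.

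**Counting**
- Section 14.3.1 reports acute and late toxicity per arm out of 12, or 6 without expansion.
- Section 14.3.4 estimates radionecrosis and symptomatic radionecrosis by cumulative incidence, with death as a competing risk and censoring at salvage whole brain radiation and/or last follow-up.
- No section defines a DLT-evaluable patient or provides for replacement.

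**The concern.** A telephone call about survival cannot establish symptomatic necrosis, which by definition needs imaging and neurological symptoms. A site that follows section 13 to the letter has no scheduled CNS reading for a patient on telephone contact. A site that follows 14.1.2 does. The plan does not say which prevails.

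The counting rule then gives the gap a direction. With a fixed denominator, an unread patient can only enter 14.3.1 as a non-event, so reported toxicity leans low. For late necrosis, the same patient is censored in 14.3.4, and the two sections can report different pictures of one arm. Late toxicity cannot stop an arm, but 14.1.2 uses it to choose the best radiation dose.

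**Working it through.** The plan gives no figure for missing CNS readings, so there is none to reproduce. Its 72% power statement concerns 1-year survival and does not bear on this point.

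**1. When telephone contact begins, against when readings fall due.** Count from cycle 1, day 1, with cycle n on day 1 + 21(n − 1). Readings fall at about days 92, 183 and 365. Take the route in section 6.5, assuming treatment stops at confirmation:
- Week-12 scan: day 84.
- Confirmation 4 to 6 weeks later: days 84 + 28 = 112 to 84 + 42 = 126.
- Last dose before confirmation: cycle 6, day 1 + 105 = 106 (cycle 7 would be day 127).

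Under 13.1.2.4.1 telephone contact starts at about day 112 to 126. That is after the 3-month reading, 57 to 71 days before the 6-month reading (183 − 126; 183 − 112) and 239 to 253 days before the 12-month reading.

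**2. What adverse event collection still picks up.** Under 13.2.3.1, serious events are collected to 90 days after the last dose, or to 30 days if new therapy starts.
- With new therapy: 106 + 30 = day 136, which is 47 days before the 6-month and 229 days before the 12-month reading.
- Without new therapy: 106 + 90 = day 196, which passes the 6-month reading but ends 169 days before the 12-month one.

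**3. The 3-month reading.** A patient who starts new therapy before day 92 loses the scheduled reading under 13.1.1.6.3. Serious event collection then ends on day 31, 52 or 73 for a last dose at cycle 1, 2 or 3, all short of day 92. After a cycle 4 dose (day 64) it runs to day 94. Only early discontinuation exposes the DLT rule.

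**4. Effect on the 3-of-6 rule (illustration).** Take a true DLT rate p = 1/3, in line with the 33% accepted in 4.6.3. Assume unread patients share that risk but are counted event-free. The chance of stopping is P(X ≥ 3), with X ~ Bin(number read, p):
- 6 read: 233/729 = 0.320.
- 5 read: 51/243 = 0.210.
- 4 read: 9/81 = 0.111.

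If half of an unread patient's risk is still captured before collection closes, the last two become 0.265 and 0.213.

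**5. Effect on the reported proportion (illustration).** Suppose 3 events with 2 of 12 unread. Section 14.3.1 gives 3/12 = 25.0% (Clopper-Pearson 95% interval 5.5 to 57.2). Among those read it is 3/10 = 30.0% (6.7 to 65.2).

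**6. How many might be unread.** The documents do not say. In the pembrolizumab-alone study in 4.4.1, 3 of 18 patients (16.7%; 95% interval 3.6 to 41.4) were not evaluable because of extracerebral progression. Their timing and later therapy are not given, and nothing is said about missing toxicity readings. It shows that such losses occur; it does not estimate their rate here.

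**The case against.** Much of the case on the other side stands.

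- **Section 6.4.2 is not the source of the telephone step.** It applies only in the screening and treatment phase, says nothing of telephone calls, and states that no therapy is prohibited in post-treatment follow-up. A patient who stops for confirmed progression and then starts another drug is outside it. The telephone step rests on 13.1.1.6.3, 13.1.2.4.1 and 10.2.
- **A reader might infer that the plan has no rule for unread patients. It has.** Section 14.3.4 censors radionecrosis at last follow-up, and 14.3.1 implies a non-event. The fault for late toxicity is that the two disagree. The rule is wholly absent only for the 3-month DLT.
- **Other text softens the gap.** Section 2.1 describes brain MRI every 3 months as standard of care, and 11.1.10 asks for toxicity evaluation every 3 months. Section 13.1.2.3 images after confirmed progression until new therapy. Section 13.1.1.13 says "all applicable activities scheduled for the final trial visit should be performed at the time of discontinuation". Salvage brain radiation alone does not end follow-up (11.1.11). Serious events judged related to the Merck product must be reported whenever they come to light (13.2.3.1).
- **The flow chart is weak evidence of contradiction.** Its layout is broken in the text available, and it has no visible survival follow-up column.

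These provisions do not close the gap. Standard-of-care imaging can go unread for the trial once only survival is asked about. Open-ended serious event reporting depends on attribution to the drug, so necrosis attributed to radiosurgery may not qualify. Adverse events above Grade 1 are followed to resolution "or until the beginning of a new anti-neoplastic therapy, whichever occurs first".

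One further objection shapes the remedy. A proportion among patients read at 12 months would drop those who died, and 14.1.2 cites 1-year survival of about 38% after radiosurgery alone. The 14.3.4 method handles death better.

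**Conclusion.** The point holds in a bounded form. Sections 13.1.1.6.3, 13.1.2.4.1 and 10.2 do not agree with 13.1.2.3, 14.1.1 and 14.1.2 on whether CNS assessment continues after progression or new therapy. The fixed denominator in 14.3.1 turns the resulting gaps into non-events. The 6- and 12-month necrosis readings are the main exposure: on the week-12 progression route both fall after telephone contact begins.

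A reader might go further and conclude that the primary safety rule is compromised. The documents do not support that. Progression first seen on the week-12 scan is confirmed after the 3-month reading, so only early discontinuation exposes the rule, and no rate of such loss is given. The fall from 32% to 21% (or 11% with two unread) rests on an assumed number unread, equal risk in those patients, and counting them event-free. The contrast of 25% with 30% is likewise an illustration, well inside either interval. The direction of the bias is clear; its size is unknown. The change is worth making because it is cheap and late toxicity informs the choice of arm.

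**What to change.** 1. **Follow-up.** In 13.1.1.6.3 and 13.1.2.4.1, with matching wording in 10.2 and 13.1.2.3, state: *after confirmed progression or new anti-cancer therapy, the 3-, 6- and 12-month CNS toxicity assessments continue, using standard-of-care visits and brain MRI; readings taken after non-protocol therapy are flagged.* In 6.4.2, replace removal from the trial with discontinuation from study treatment.
2. **DLT rule.** In 14.1.1, state: *a patient with no 3-month reading and no earlier DLT is not counted as DLT-free in the 3-of-6 rule.*
3. **Late toxicity.** In 14.3.1, make the 14.3.4 cumulative incidence the main estimate, with death as a competing risk and censoring at the last CNS assessment. The present term, last follow-up, is also used for survival in 14.3.3 and could be read as the last telephone call. Report the number unread per arm beside the fixed-denominator proportion.

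The cost is mostly wording, since the visits and scans are already standard of care. Some later readings will be confounded by the new therapy, hence the flag, and reported toxicity may look slightly less favourable. Item 2 can leave the rule undecided. With one of six unread, this happens when exactly 2 of the 5 read have a DLT: 10p²(1 − p)³ = 0.098 at p = 0.12 (the radiosurgery-alone rate in 4.6.3) and 0.329 at p = 1/3. A replacement patient would then settle it.
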